## 1.4 CLINICAL EXPERIENCE

### 1.4.1 Clinical Pharmacokinetics

Following a single oral dose of belumosudil 200 mg in the fed state, the mean absolute bioavailability (%F) was 64%. Systemic exposure of belumosudil was increased when administered in the fed state, and in ongoing and planned clinical studies, belumosudil should be taken with food or within 5 minutes of eating.

Across all clinical studies, observed time to reach maximum concentration for belumosudil, belumosudilm1, and belumosudilm2 has ranged from 2-4 hours, and the belumosudil terminal elimination half-life averages ~7 hours following single or multiple dose administration. Exposure of belumosudil (maximum concentration observed and area under concentration curve) in healthy subjects appears to be slightly greater than dose proportional over the 20 to 500 mg once daily (QD) dose range, but less than dose proportional for doses above 500 mg. Little to no accumulation of belumosudil or metabolites, KD025m1 or KD025m2, was observed following multiple dose administration. KD025m1 and KD025m2 exposures are < 5% and ≤ 20%, respectively, of belumosudil exposure.

A [C]-belumosudil human absorption, metabolism, and excretion study confirmed that the majority of radioactivity was recovered in feces (85%), with < 5% recovered in urine. This indicates minimal renal elimination and that the predominant route of clearance of belumosudil and associated metabolites is biliary and/or intestinal.

Cytochrome P450 3A4 (CYP34A) likely plays a predominant role in the metabolism of belumosudil, and in a clinical drug-drug interaction study in healthy volunteers, co-administration with itraconazole (CYP3A4 inhibitor) resulted in a modest 20-25% increase in belumosudil exposure, while co-administration with rifampicin (CYP3A4 inducer) led to a 60-70% reduction in belumosudil exposure.

A delay in absorption and a reduction in belumosudil exposure were observed when belumosudil was co-administered with proton pump inhibitors (PPI) rabeprazole (80-90% decrease) or omeprazole (50-70% decrease), consistent with the finding that increased pH leads to decreased solubility of belumosudil. The clinical relevance of this interaction with PPIs is being evaluated in ongoing studies.

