## 1.6 DOSE RATIONALE

Belumosudil was well-tolerated in Phase 1 studies of healthy volunteers at single doses up to 1000 mg, and with repeat doses up to 500 mg BID for 28 days.

Phase 2 studies of belumosudil have been initiated, enrolling patients with IPF (KD025-207), cGVHD (Study KD025-208 and Study KD025-213) and psoriasis (Study KD025-205, Study KD025-206, and Study KD025-211). More than 600 subjects have been dosed with belumosudil for inflammatory or fibrotic diseases or as healthy volunteers at doses ranging from 20 mg to 1000 mg QD and 500 mg BID.

Preliminary data from phase 2 studies of belumosudil indicate that the dose of 200 mg QD is associated with clinical efficacy and should be well-tolerated in an indication with immune and fibrotic manifestations (e.g., diffuse cutaneous systemic sclerosis [dcSSc]).

This study will evaluate belumosudil at a dose of 200 mg BID in an open study in dcSSc to further evaluate safety and activity.

Also, refer to the [Belumosudil IB](#) for more detailed information.

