#### **4.9 CYP3A4 INHIBITORS/INDUCERS**

CYP3A4 inhibitors/inducers should be used with caution ([Appendix G](#)).

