## 7. PHARMACOKINETICS

No pharmacokinetic analysis to be performed in this study.

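### CYP3A4 inducers and inhibitors share one caution rule although the protocol reports a 60-70% exposure loss for one and a 20-25% rise for the other; strong inducers could be barred at small cost

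*Protocol*

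**What the plan says.** - **Interaction data.** Protocol 1.4.1 describes a study in healthy volunteers in which "co-administration with rifampicin (CYP3A4 inducer) led to a 60-70% reduction in belumosudil exposure". The effect in the other direction was much smaller: "co-administration with itraconazole (CYP3A4 inhibitor) resulted in a modest 20-25% increase in belumosudil exposure".
- **Rule.** Section 4.9 reads "CYP3A4 inhibitors/inducers should be used with caution", and the synopsis says the same under Concomitant Treatment. Appendix G names 12 inducers (6 strong, 4 moderate, 2 weak). It asks that co-medications be checked for interactions but states no action.
- **Contrast.** QTc-prolonging drugs are prohibited outright (exclusion 2, section 4.10, Appendix H). None of the 12 inducers appears in Appendix H, and no exclusion criterion in 3.5 names an inducer.
- **Measurement.** Section 7 states "No pharmacokinetic analysis to be performed in this study"; the synopsis and section 9.10 agree. Appendix A has no row for PK samples.
- **Compliance and medication data.** SAP 3.7 defines relative dose intensity (RDI) from milligrams taken over milligrams planned. SAP 3.6 lists and summarises concomitant medications.
- **Dose.** Section 1.6 says that "the dose of 200 mg QD is associated with clinical efficacy"; this study uses 200 mg BID.
- **PPIs.** Section 1.4.1 also reports losses of 50-70% with omeprazole and 80-90% with rabeprazole, and adds: "The clinical relevance of this interaction with PPIs is being evaluated in ongoing studies". The protocol sets no rule for PPIs.

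**The concern.** One instruction covers two effects that differ in direction and in size. An investigator who reads 4.9 is not told that the inducer side may remove most of the delivered exposure while the inhibitor side adds about a quarter. The protocol does prohibit drugs where it wants to, so leaving strong inducers out is a choice and not a limit of the format.

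The counselling in section 4.8 covers non-prescribed and complementary products that the study excludes. St. John's wort is a strong inducer in Appendix G but is on no exclusion list, so it is unclear whether the counselling reaches it.

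The study has one arm and 12 to 15 subjects, and section 9.7.1 says it is meant to guide follow-up studies. A subject with much reduced exposure who does not respond could be read as a failure of the drug at 200 mg BID. The medication listing would show who took an inducer, but nothing would show how much exposure was lost.

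**Working it through.** There is no sample-size or power figure to reproduce: 12 to 15 subjects is not based on a test, and the interaction percentages are reported results without underlying data.

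**Inputs.** Loss with rifampicin L = 0.60 to 0.70; rise with itraconazole 0.20 to 0.25; "Little to no accumulation of belumosudil or metabolites" on repeat dosing (all 1.4.1). Planned dose 200 mg BID (4.2). Tolerated in healthy volunteers: "with repeat doses up to 500 mg BID for 28 days" (1.6).

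**Assumption.** Section 1.4.1 uses the word exposure for both maximum concentration and AUC. The 60-70% is treated here as an AUC loss.

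**Unit.** AUC of one uninduced 200 mg dose. Every dose is 200 mg under both regimens and accumulation is slight, so dose proportionality is not needed for the BID and QD comparison.

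| Situation | Daily exposure | Share of planned BID |
|---|---|---|
| 200 mg BID, no interaction | 2 x 1 = 2.0 | 100% |
| 200 mg QD, no interaction | 1.0 | 50% |
| BID with rifampicin-strength inducer | 2 x 0.40 = 0.8 to 2 x 0.30 = 0.6 | 40% to 30% |
| BID with itraconazole | 2 x 1.20 = 2.4 to 2 x 1.25 = 2.5 | 120% to 125% |
| BID with omeprazole | 2 x 0.50 = 1.0 to 2 x 0.30 = 0.6 | 50% to 30% |
| BID with rabeprazole | 2 x 0.20 = 0.4 to 2 x 0.10 = 0.2 | 20% to 10% |

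**Fold change.** Inducer: 1/(1 - 0.60) = 2.5 to 1/(1 - 0.70) = 3.3. Inhibitor: 1.20 to 1.25.

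**Break-even with QD.** 2 x (1 - L) = 1 gives L = 0.50. The documents give no loss for carbamazepine, phenytoin or St. John's wort. Assumed losses of 20%, 40%, 50% and 70% give 1.6, 1.2, 1.0 and 0.6, so BID falls below QD only if the loss exceeds 50%.

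**Duration.** With w of the first 24 weeks on the inducer, ignoring onset and offset, mean share of planned exposure = 1 - L x w/24.
- w = 4: 90.0% (L = 0.60) or 88.3% (L = 0.70)
- w = 12: 70% or 65%
- w = 24: 40% or 30%
- A share below 50% needs w > 24 x 0.5/0.7 = 17.1 weeks or 24 x 0.5/0.6 = 20.0 weeks.

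Only long-term use brings the mean below the QD level.

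**RDI.** All tablets taken: 100 x 400/400 = 100%, whatever the inducer does. A toxicity reduction to 200 mg QD throughout would read 100 x 200/400 = 50%.

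**Inhibitor side.** Exposure is slightly more than proportional up to 500 mg, so 500 mg BID is at least 2 x 2.5 = 5.0 units. Itraconazole gives at most 2.4/5.0 = 48% to 2.5/5.0 = 50% of that, so caution is a reasonable rule there.

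**Weight of one subject.** 100/12 = 8.3 or 100/15 = 6.7 percentage points of the CRISS60 rate.

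**The case against.** **No consequence is shown.** No document says that any subject will take a strong inducer. Chronic GVHD response was 65% at 200 mg QD, 69% at 200 mg BID and 33% at 400 mg QD (1.4.1.1), which shows no clear gain from more drug. The psoriasis PASI 75 rates cannot serve as a benchmark either, because placebo reached 16.7% (1.4.1.3). This stands, and it caps the weight of the point.

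**The pool of users is small.** A positive tuberculin test is excluded, which makes rifampicin unlikely at entry. The malignancy exclusion would largely remove enzalutamide and mitotane, assuming oncology use. That leaves carbamazepine, phenytoin and St. John's wort, for which the documents give no figure. This also stands.

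**Some of it is already handled.** Appendix G asks for an interaction check, exclusion 5 allows judgement, the Investigator's Brochure (not available here) may say more, and users can be identified from the listings. These reduce the risk but do not tell sites what to do with a strong inducer.

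**PPIs are the larger loss.** On the same scale rabeprazole leaves 0.2 to 0.4 units against 0.6 to 0.8 for rifampicin, and PPIs have no rule at all. This is fair. Section 1.4.1 calls the relevance of the PPI interaction unresolved and makes no such statement for inducers. Barring one and counting the other is therefore a judgement, but the count should be required.

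**Direction.** Lower exposure would tend to understate efficacy and not to create a false positive. Agreed.

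**Conclusion.** The mismatch between the interaction data and the rule is real, and a stricter rule for strong inducers is a cheap improvement. It concerns concomitant medication and eligibility; no analysis is wrong. It is a change to consider, not one on which the trial depends.

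The size is conditional: 30-40% of planned exposure for a subject who takes a rifampicin-strength inducer throughout, if the 60-70% is an AUC loss and carries over from healthy volunteers.

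A reader might infer more than this, and the documents do not support it:
- **That CRISS60 will be biased.** The number of users may be zero, and similar QD and BID responses in chronic GVHD mean the effect may be nil.
- **That induced subjects fall below an effective dose.** Section 1.6 links 200 mg QD to efficacy but does not call it a minimum.
- **That every strong inducer costs 60-70%.** The figure is for rifampicin only.
- **That RDI is wrongly defined.** It is a sound measure of tablets taken; it simply cannot show this loss.
- **That the text rules out PK sampling.** It rules out PK analysis. The absence of samples is read from Appendix A.

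**What to change.** 1. **Section 4.9 and synopsis.** Replace the caution sentence with: *Strong CYP3A4 inducers (Appendix G), including St. John's wort, are not permitted from 14 days before Day 1 through the last dose of study drug. Inhibitors and moderate or weak inducers of CYP3A4 require caution.* The 14 days is an example for the sponsor to confirm. With 14 days, last use must be by Day -15, which fits inside the Day -29 to -1 screening window.
2. **Section 3.5 and synopsis.** Add a matching exclusion for use of a strong inducer within that washout. State that a needed prescribed medicine is not to be stopped only to qualify. The counselling in 4.8 then clearly covers St. John's wort.
3. **Section 4.9.** Add that unavoidable use on study is recorded as a deviation with dates, goes to the medical monitor for a decision on continuation, and leaves the subject in the mITT Population.
4. **SAP 3.6.** Require two separate descriptive counts from Day 1 to Week 24: subjects who took a strong inducer, and subjects who took a PPI.

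**Cost.** Five protocol edits (items 1 and 2 in two places each, item 3 in one) in one amendment that needs IRB/IEC approval under section 12, and one SAP edit that uses data already collected. A candidate who needs carbamazepine or phenytoin may be lost from a study of 12 to 15 subjects. Losses from PPIs would be described, not prevented.

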#### **1.4.1.1 Chronic Graft Versus Host Disease**

KD025-208 is an ongoing phase 2a, dose-escalation, open-label study to evaluate the safety, tolerability, and activity of belumosudil in subjects with cGVHD who have previously received 1-3 prior lines of treatment. The majority of subjects enrolled had cGVHD affecting at least 4 organs. Preliminary data from Cohort 1 (200 mg QD, n = 17), Cohort 2 (200 mg twice daily [BID], n = 16), and Cohort 3 (400 mg QD, n = 18) show encouraging activity of belumosudil with response rates of 65%, 69% and 33%, respectively. Responses have been durable. Among responders in Cohort 1, 8/11 (73%) have sustained the response for  $\geq$  20 weeks. Data continue to mature in this ongoing study. Fifty-nine (59%) of subjects have achieved reductions in corticosteroid doses, with 10% discontinuing systemic corticosteroid therapy completely. Across the 3 cohorts, 61% of responders and 26% of non-responders have reported improvements in the Lee Symptom Scale score. KD025-213 is another study in cGVHD which is currently ongoing at multiple sites in the U.S. Over one hundred subjects have been enrolled and this study will be submitted as a potential registration study for cGVHD in 2020.

#### **1.4.1.2 Idiopathic Pulmonary Fibrosis**

KD025-207 is an ongoing, randomized, phase 2, open-label, multicenter study to evaluate the safety, tolerability, and activity of belumosudil in subjects with IPF who have received pirfenidone and/or nintedanib or been offered both prior to enrollment. Subjects are randomized 2:1 to receive 400 mg belumosudil QD or best supportive care (BSC).

Forty subjects have been enrolled: 26 to the belumosudil arm and 14 subjects to the BSC arm. Nine BSC subjects have crossed over to the belumosudil arm. This study has been extended to enroll an additional 40 subjects.

Preliminary results demonstrate clinical activity of belumosudil in the treatment of IPF. In the modified intent to treat (mITT) population, there was an absolute median change in forced vital capacity (FVC) of 50 mL at Week 24 in subjects treated with belumosudil, compared to -175 mL in subjects treated with BSC. The decline in percentage predicted FVC was 1% with belumosudil versus 5% with BSC.

Overall, at Week 24, 29% of belumosudil patients had experienced an FVC decline  $\geq 5\%$ , compared to 55% of BSC patients.

#### **1.4.1.3 Psoriasis**

In KD025-205, a study of 8 subjects with moderately severe psoriasis who had failed at least 1 line of systemic therapy, the mean Psoriasis Area and Severity Index (PASI) score decreased with 28 days of treatment by 1.1 (not statistically significant) from a mean baseline of 17.5. Some subjects experienced slight improvement in scaling and softening of plaques.

KD025-206 was a phase 2, open-label, safety and tolerability study of belumosudil dosing in 38 subjects with psoriasis vulgaris who had disease progression after at least one systemic therapy. The mean baseline PASI score was 19.8. The changes from baseline PASI scores were -8.8 (belumosudil 200 mg), -6.0 (belumosudil 400 mg QD) and -4.8 (belumosudil 400 mg BID) and were statistically significant for each treatment group and overall. Reductions of 50% in PASI scores were observed in 42% (200 mg BID), 50% (400 mg QD), and 18% (400 mg BID) of subjects.

KD025-211 was a Phase 2, two-period, dose-finding study of the safety, tolerability, and efficacy of belumosudil for the treatment of adult male and female subjects with moderate to severe chronic plaque psoriasis who were candidates for systemic therapy or phototherapy.

The first period (Week 1 through Week 16) was double-blind and placebo-controlled: the Double-blind Treatment Period. Approximately 110 subjects were randomly assigned to each of 5 dose cohorts in a 1:1:1:1:1 manner and were treated for up to 16 weeks ([Table 1](#)).

**Table 1      Cohorts (Treatment Groups) in KD025-211 Study Design**

Cohort	Number of Subjects	Dose
1	22	200 mg belumosudil QD
2	22	200 mg belumosudil BID
3	22	400 mg belumosudil QD
4	22	600 mg belumosudil (400 mg in the morning; 200 mg in the evening)
5	22	Matching placebo BID

BID = twice daily; QD = once daily

Study drug was administered orally (PO), with a meal or within 5 minutes of finishing a meal, in a double-blind fashion.

The second period (Week 16 through Week 52) was an open-label study of belumosudil: the Open-label Treatment Period. All subjects were given the option to receive belumosudil for an additional 32 weeks. All subjects in the Open-label Period received belumosudil at 400 mg QD, regardless of initial randomization.

Subject status was collected at screening, Week 1 Day 1 (baseline), and for the evaluation of primary and secondary study endpoints. Response was assessed by PASI, PGA, and DLQI scores at scheduled time points throughout the study.

Subjects underwent medical history evaluations; physical examinations ([PEs] including weight, skeletal, and neurological measurements); vital sign measurements; adverse event (AE) assessments; concomitant medication assessments; blood sample collection for hematology, chemistry, coagulation, lipid panel, and thyroid-stimulating hormone; urinalysis; pregnancy testing for females of childbearing potential; photography (optional); punch biopsy (optional); and electrocardiogram (ECGs).

If a subject discontinued from the study prior to 16 weeks, an Early Termination Visit was performed, and procedures were conducted immediately upon discontinuation. For

all subjects, including those who discontinued from the study prematurely, a Follow-Up Visit occurred 30 days ( $\pm$  3 days) after the last dose of study drug.

A placebo control was used in the Double-blind Period of this study. No control was used for the Open-label Continuation Period of the study.

A total of 110 subjects were randomized and included in the mITT Population: 23 subjects in the belumosudil 200 mg QD cohort, 22 in the belumosudil 200 mg BID cohort, 21 in the belumosudil 400 mg QD cohort, 26 in the belumosudil 600 mg/day cohort, and 18 in the placebo cohort. The Safety Population had the same number of subjects as the mITT Population. Of the 110 subjects in the study, 27.3% (n = 30 subjects) completed treatment: 39.1% (n = 9) in the belumosudil 200 mg QD cohort; 27.3% (n = 6) in the 200 mg BID cohort; 42.9% (n = 9) in the 400 mg QD cohort; 15.4% (n = 4) in the 600 mg/day cohort; and 11.1% (n = 2) in the placebo cohort. Overall, the most frequent reasons for early study termination were withdrawal by subject (40.9%; n = 45 subjects), followed by loss to follow-up (12.7%; n = 14 subjects), and elevated liver enzymes (5.5%; n = 6 subjects).

The primary efficacy end point was the number (%) of subjects with a 75% decrease in PASI (PASI 75) by Week 16. When including subjects who completed 16 weeks of treatment and carrying forward the last results of subjects who did not complete 16 weeks of treatment, all belumosudil-treated subjects and all belumosudil cohorts had a proportion of subjects with PASI 75. Among all 92 KD025-treated subjects, 10.9% (95% confidence interval [CI]: 5.3%, 19.1%; n = 10 subjects) had a PASI 75 at Week 16. Of the 18 subjects in the placebo cohort, 16.7% (95% CI: 3.6%, 41.4%; n = 3 subjects) had a PASI 75. Each belumosudil cohort had a proportion of subjects with PASI 75: 8.7% (95% CI: 1.1%, 28.0%; 2/23 subjects) in the 200 mg QD cohort; 9.1% (95% CI: 1.1%, 29.2%; 2/22 subjects) in the 200 mg BID cohort; 19.0% (95% CI: 5.4%, 41.9%; 4/21 subjects) in the 400 mg QD cohort; and 7.7% (95% CI: 0.9%, 25.1%; 2/26 subjects) in the 600 mg/day cohort. The proportion of subjects who had a PASI 75 among all belumosudil-treated subjects was less than for placebo (-5.8% [95% CI: -24.2%, 12.6%]) but the difference was not statistically significantly different (p = 0.4435). None of the belumosudil-treated cohorts had a statistically significant difference compared to the placebo cohort: p = 0.6384 for the 200 mg QD cohort; p = 0.6419 for the 200 mg BID cohort; p > 0.9999 for the 400 mg QD cohort; and p = 0.3859 for the 600 mg/day cohort.

During the Entire Treatment Period, 92 subjects received belumosudil and 18 subjects received placebo. The proportions of TEAEs among all 92 KD025-treated subjects were comparable to or less than those occurring among the 18 subjects in the placebo cohort were as follows:

- Severe TEAE: belumosudil = 8.7% (n = 8 subjects); placebo = 11.1% (n = 2 subjects)
- Grade  $\geq$  3 TEAEs: belumosudil = 10.9% (n = 10); placebo = 11.1% (n = 2)
- TEAEs related to study drug: belumosudil = 30.4% (n = 28); placebo = 33.3% (n = 6)
- Grade  $\geq$  3 TEAEs considered related to study drug: belumosudil = 5.4% (n = 5); placebo = 5.6% (n = 1)
- Grade 4: belumosudil = 1.1% (n = 1); placebo = 0
- SAEs: belumosudil = 4.3% (n = 4); placebo = 5.6% (n = 1)
- SAEs related to study drug: belumosudil = 0; placebo = 0
- TEAEs leading to discontinuation: belumosudil = 16.3% (n = 15; includes SAE); placebo = 16.7% (n = 3)
- Deaths: belumosudil = 1.1% (n = 1); placebo = 0
- Deaths related to study drug = 0

The conclusions of the study were that PO administration of belumosudil improves the clinical symptoms of subjects with psoriasis as demonstrated by:

- Improvement in PASI 75 score at 16 weeks, regardless of dosing regimen
- Improvement in PASI 75 score at 48 weeks
- Improvement in DLQI score at 16 weeks
- Improvement in DLQI score at 48 weeks
- Generally well-tolerated with no deaths or SAEs considered related to study drug

#### **1.4.1.4 Other Potential Indications**

Other potential indications include bronchiolitis obliterans and solid organ transplantation.

In addition to being a pulmonary manifestation of cGVHD, bronchiolitis obliterans is a form of chronic lung allograft dysfunction that affects a majority of lung transplant recipients and is the principal factor limiting long-term transplant survival. Bronchiolitis obliterans is characterized by progressive airflow obstruction unexplained by acute rejection, infection, or other coexistent condition.

Recent data have implicated IL-17 and Th17 cells in the development of autoimmunity and chronic rejection after lung transplantation in both animal models and humans. A correlation between decreased regulatory T cells and the incidence of bronchiolitis obliterans has been reported in lung transplantation recipients.

There remains substantial unmet medical need for therapies for patients with bronchiolitis obliterans.

The goal of achieving prolonged graft survival in the absence of immunosuppression has long been an aspiration of transplant physicians and researchers. One approach for inducing immune tolerance has been combined kidney and hematopoietic stem cell transplant. Upregulation of the Treg cells may result in higher levels of donor chimerism and lead to prolonged graft survival in the absence of immunosuppression in the HLA mismatched setting.

#### **1.4.2 Clinical Summary**

As of 19 February 2020, more than 600 individuals have been dosed with belumosudil as participants of phase 1 and phase 2 Kadmon-sponsored studies.

Single and multiple doses of belumosudil up to 1000 mg appear to be safe and well tolerated in phase 1 studies conducted in healthy volunteers. There were few SAEs, all unrelated to belumosudil. The most common AEs seen in Phase 1 studies were transient increases in transaminases which resolved after cessation of dosing.

Analysis of Phase 2 safety data from subjects with cGVHD, IPF, and psoriasis suggests an acceptable, manageable safety profile for belumosudil. Overall, TEAEs have generally been consistent with those expected in the populations enrolled in each of the studies.

Development of belumosudil is most advanced in the indication of cGVHD. Data from an early Phase 2 study, KD025-208, served as the basis for a Breakthrough Therapy Designation for belumosudil for the treatment of adult patients with cGVHD. These

---

results were also the basis for a subsequent study, KD025-213 (the ROCKstar Study). Subjects who had received 2 to 5 prior lines of systemic therapy for cGVHD were enrolled into the ROCKstar study, a population with significant unmet medical need. Overall, 132 subjects were randomized to receive either belumosudil 200 mg QD (Arm A, n=66) or belumosudil 200 mg BID (Arm B, n=66). Subjects enrolled reflected a real-world population of complex, advanced cGVHD patients: median age 56 years; male 57%; 49% had received at least 4 prior lines of systemic therapy; median time from transplant to study 29 months; severe cGVHD at baseline 67%; prior treatment with ibrutinib 35%. The primary endpoint was met in both dosing arms at the primary analysis (6 months after last patient enrolled): overall response rate (95% CI on a mITT basis was 73.5% (95% CI: 65%, 81%).

Taken together, the totality of the data support the continued development of belumosudil.

